13.6. Respiratory Assessments

13.6.1. Asthma Control Test

Subjects with a medical history of asthma will take an Asthma Control Test (ACT) at Baseline/Day 1, Week 4, Week 8, Week 12, Week 16, Week 20 and Week 24, Early Termination visit, and Week 32/Follow-up. Subjects with new (de novo) diagnosis of asthma will complete the ACT testing beginning from new (de novo) diagnosis and at all subsequent scheduled visits.

The ACT is composed of 5 questions. For each question, the subject will choose the best answer out of 5 possible answers. The test provides a numerical score ranging from 5 to 25 to assess asthma control; a higher score indicates better asthma control while a score of 19 or less indicates the subject's asthma may not be under control.

ACT total score (absolute values and change from Baseline) will be summarized as a continuous variable (Baseline and scheduled visits only).

The number and percentage of subjects with an ACT score ≤ 19 will be summarized (scheduled visits only).

The ACT results and the ACT score will be listed on the Safety population.

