### 10.3.2 Unscheduled Visit

The subject should be reminded to adhere to the study schedule. Unscheduled visits are defined as visits to repeat testing for abnormal laboratory results, for follow-up of AEs, or to conduct efficacy assessments for subjects requiring rescue medication between regularly scheduled study visits. Visits occurring outside of the visit window are not considered unscheduled visits.

Assessments to be conducted at the unscheduled visit will depend on the reason for the visit: any of the procedures/assessments listed in [Table 7](#) may be conducted, but not all are required. Blood sample collection for POE and ADA analyses are required during unscheduled visits that are conducted for safety reasons when safety labs are collected for the management/monitoring of an AE. When a series of unscheduled visits is needed for the monitoring of the same AE, the POE and ADA collection is not required if already done at the first unscheduled visit of the series. Additional collection of samples for POE and ADA analysis should be performed per Investigator's judgment.

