Week 21	148	141 to 147	142 to 148
Week 22	155	148 to 154	149 to 155
Week 23	162	155 to 161	156 to 162
Week 24 ^a	169	162 to 175	163 to 176
Early Termination*	UN	7 days prior until Early termination visit (excluding early termination visit date)	6 days prior until early termination visit (including early termination visit date)

^a First 7 days data available will be used for weekly average calculation.

*For subjects with early termination, if weekly average is not available based on the slotting, additional analysis window was added and will be assigned to the week based on the slotting above. i.e., if subject

This document is confidential.

early terminated day 142, and week 21 is not available, the new window defined will be used to determine the weekly average at that week.

Safety and pharmacokinetics data will not be windowed for by-visit summary. i.e., scheduled visit data will be used for analysis.

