13.2.1. Clinical Laboratory Evaluations

The hematology laboratory analyses, clinical chemistry laboratory analyses, and urinalyses will be performed at a central laboratory. Reference ranges will be supplied by the central laboratory and used by the investigator to assess the laboratory data for clinical significance and pathological changes. Reference ranges will be provided in the laboratory manual.

The following parameters will be reported for laboratory data.

- **Hematology:** Hemoglobin, hematocrit, white blood cell (WBC) count (with differential including eosinophils), red blood cell (RBC) count, platelet count, and mean cell volume (MCV).
- **Chemistry:** Creatinine, aspartate aminotransferase (AST), alanine aminotransferase (ALT), gamma glutamyl transferase, alkaline phosphatase, lactate dehydrogenase, total bilirubin, direct bilirubin, albumin, total protein, uric acid, sodium, potassium, calcium, chloride, glucose, urea, total cholesterol, triglycerides, low-density lipoprotein, high-density lipoprotein, creatine phosphokinase (CPK). CPK isoenzyme test will be performed only if CPK is elevated to $>2.5 \times$ upper limit of normal (ULN).
- **Urinalysis:** pH, glucose, ketones, blood, protein, leukocytes, nitrites, bilirubin, urobilinogen, and specific gravity.

Laboratory assessments are performed at Baseline/Day 1, Week 12, Week 24, Early Termination and Week 32/Follow-up.

Hematology and chemistry laboratory data (absolute values and change from Baseline) will be summarized as continuous variables by visit (Baseline and scheduled visits only). Urinalysis laboratory data will be summarized by visit (Baseline and scheduled visits only). Last post-baseline, worst post-baseline and maximum post-baseline results will also be included in the summaries and will include unscheduled visits

This document is confidential.

in the derivation. Worst post-baseline value will be defined as the highest or lowest value relative to the reference range. Parameters will be presented in alphabetically order.

Shift tables will be generated using the reference ranges (Low, Normal, High and Missing) for hematology and chemistry laboratory data. The number and percentage of subjects shifting from reference ranges between Baseline and each visit (scheduled visits only) will be summarized. Last, worst and maximum post baseline values will also be included in the shift tables and will include unscheduled visits in the derivation.

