13.4. ECG

A 12-lead electrocardiogram (ECG) will be performed and read centrally at Baseline/Day 1, Week 24 and Early Termination visit.

All ECG data (absolute values and change from Baseline) will be summarized as continuous variables by visit (Baseline and scheduled visits only). All parameters will be presented in alphabetically order.

The overall results of the ECGs recorded as 'Normal', 'Abnormal, NCS' or 'Abnormal, CS' will be summarized by treatment group and visit (scheduled visit only). Clinical significance will be determined by the investigator.

Additionally, all ECG findings will be summarized with numbers and percentages by visit (Baseline and scheduled visits only).

All ECG results will be listed on the Safety population.

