13.6.3. Peak Expiratory Flow

Peak expiratory flow (PEF) testing during the clinical study will be performed under the supervision of qualified study personnel. Peak expiratory flow measurements should consist of 3 good efforts, with the best result documented. Obtained PEF values will be compared to predicted values based on the subject's age, sex and height.

PEF testing will be performed for all subjects at Baseline/Day 1, Week 12, Week 24, Early Termination, and Week32/Follow-up visits. For subjects reporting a medical history of asthma, PEF testing will be performed at all visits during the clinical study. For subjects diagnosed with new (de novo) asthma, PEF testing will be performed at all visits, starting with the visit in which the diagnosis was confirmed.

Following PEF parameters will be summarized as a continuous variable (Baseline and scheduled visits only):

- Actual peak expiratory flow rate
- Predicted peak expiratory flow rate
- Actual PEF of predicted value (%).

These PEF parameters will be summarized separately for the subset of subjects with and without history of asthma.

The number and percentage of subjects with PEF < 80% will be summarized by treatment group, visit (baseline and scheduled visits only), and medical history of asthma (with and without history of asthma).

All PEF results will be listed on the Safety population.

This document is confidential.

14. Changes from Analysis Planned in Protocol

- Summary Statistics will be presented by Treatment Group instead of “by Treatment Group and dosing regimen”.

This document is confidential.

15. Programming Considerations

All TFLs and statistical analyses will be generated using SAS® 9.4 or higher (SAS® Institute Inc., Cary, NC, USA) on a SAS Server. Changes to the software version (e.g. upgrades), or use of additional software consistent with the SAP will not be considered a violation of the SAP.

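### The ACT ≤19 and PEF <80% counts use scheduled visits only and have no any-time or worst post-baseline row, so a crossing measured only at an unscheduled visit is missing from those summary tables

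*SAP*

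**What the plan says.** SAP 13.6.1 limits both ACT summaries to scheduled visits. For the threshold count: "The number and percentage of subjects with an ACT score ≤ 19 will be summarized (scheduled visits only". For the score itself: "ACT total score (absolute values and change from Baseline) will be summarized as a continuous variable (Baseline and scheduled visits only". SAP 13.6.3 does the same for PEF: "The number and percentage of subjects with PEF < 80% will be summarized by treatment group, visit (baseline and scheduled visits only", with a further split by asthma history. SAP 8.4 closes the other way in: "Safety and pharmacokinetics data will not be windowed for by-visit summary. i.e., scheduled visit data will be used for analysis". An unscheduled reading therefore cannot be slotted into a nearby visit, as efficacy data can.

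Protocol 10.3.2 explains why unscheduled visits happen: "Unscheduled visits are defined as visits to repeat testing for abnormal laboratory results, for follow-up of AEs". On what may be measured there: "Assessments to be conducted at the unscheduled visit will depend on the reason for the visit: any of the procedures/assessments listed in" Table 7, and that table marks ACT and PEF as optional at such visits.

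Laboratory data are handled differently. SAP 13.2.1 says: "Last post-baseline, worst post-baseline and maximum post-baseline results will also be included in the summaries and will include unscheduled visits".

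**The concern.** New or worsening asthma is one of the important potential risks named in Protocol 5.3. That section also reports asthma flares rising with dose in an earlier atopic dermatitis study, from 1.8% on placebo to 12.3% at 30 mg and 17.5% at 90 mg. For subjects with a history of asthma, ACT ≤19 and PEF <80% of predicted are the protocol's own referral triggers (Protocol 12.6.4). For other subjects, a PEF result that suggests declining respiratory health prompts referral.

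A visit made because of a respiratory complaint is a likely occasion for a low reading, and that is the kind of visit the counts leave out. A subject who is below the threshold at such a visit and above it at the next scheduled one appears in the tables as never having crossed. These counts are the one comparative asthma summary that does not depend on whether someone decided to report an event, so leaving out such readings weakens them as a check on the event tables.

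**Working it through.** The plan gives no figure to reproduce. The check compares the planned rows and then sizes one missed subject.

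**1. Rows planned for each safety measure**

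| Measure (SAP section) | By-visit rows | Extra row that takes in unscheduled visits |
|---|---|---|
| Laboratory (13.2.1) | Baseline and scheduled | Last, worst and maximum post-baseline |
| Vital signs (13.3) | Baseline and scheduled | Last post-baseline in the tables; maximum in boxplots only |
| ECG (13.4) | Baseline and scheduled | None |
| Physical examination (13.5) | Baseline and scheduled for the category counts; no limit stated for the shift summary | None |
| ACT (13.6.1) | Scheduled (baseline also, for the score) | None |
| PEF (13.6.3) | Baseline and scheduled | None |

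**2. How long a crossing can go unseen**

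- Subjects with asthma have ACT and PEF at every scheduled visit, so the interval is 4 weeks up to Week 24.
- Subjects without asthma have routine PEF at baseline, Weeks 12, 24 and 32, and early termination. The intervals are 12, 12 and 8 weeks. The Week 32 visit applies only to subjects who do not continue nemolizumab in the extension study (Protocol 7.1). A fall that starts and recovers inside an interval can be measured only at an unscheduled visit.

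**3. What one missed subject is worth**

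Formula: 100 × 1/n, where n is the number of subjects with an observation. This is the default percentage denominator in SAP 15.2.5.2.

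- PEF, all subjects, about 40 randomized 1:1 (SAP 4.3): n = 20, so 100/20 = 5 points.
- PEF, all subjects, about 100 randomized 1:1 (SAP 4.1): n = 50, so 100/50 = 2 points.
- In the PEF tables split by asthma history, n is smaller and the step larger.
- ACT: only subjects with asthma complete it, and the documents do not give their number. Purely as an assumption, if 10% to 30% of a 20-subject arm have asthma, n is 2 to 6 and the step is 100/6 ≈ 17 to 100/2 = 50 points. With 50 per arm, n is 5 to 15 and the step is 100/15 ≈ 7 to 100/5 = 20 points.

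The two planned totals in the SAP differ, so both are shown. No document gives the expected number of missed subjects.

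**4. Early termination**

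SAP 13.4, 13.6.1 and 13.6.3 list early termination as a planned time point, and SAP Table 4-1 gives it a column separate from unscheduled visits. However, SAP 8.4 groups early-termination with unscheduled visits when it windows efficacy data, and no section says whether early termination counts as scheduled in safety tables. Subjects who relapse leave the study and should complete that visit (Protocol 7.1), so the point needs stating.

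**The case against.** **Asthma safety is covered elsewhere.** Asthma events go into the AESI tables and the adjudicated-event tables whatever the visit type. The scheduled respiratory examination asks about asthma, wheeze, dyspnea and cough since the last visit, and Table 14.3.4.4.11 summarizes it. ACT and PEF values are listed, and Listing 16.2.8.2.8 picks out subjects with a drop of at least 15% in either. All of this stands. It rules out the inference that asthma signals, or the readings themselves, are lost. It does not replace the count: a low ACT or PEF becomes an AESI only on the investigator's judgment (Protocol 12.7.2), listings give no comparison between arms, and the 15% listing uses a different criterion.

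**By-visit display is normal and was planned.** The protocol synopsis foresees tables by treatment group and visit, and Protocol 14.4 plans only a listing for ACT, so the SAP already does more. This also stands. The gap is the absent overall row.

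**Respiratory measures are not singled out.** A reader might infer that only respiratory and ECG data lose their worst moments. The comparison above does not support that. Physical-examination counts are restricted too, and the vital-sign tables add only a last value, which can also miss a transient excursion.

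**ECG.** The plan says: "All ECG data (absolute values and change from Baseline) will be summarized as continuous variables by visit (Baseline and scheduled visits only". A reader might infer that everyone who relapses before Week 24 has no post-baseline ECG in the tables. That requires treating a planned, named visit as unscheduled, which is the less natural reading. Clinically significant ECG and examination changes are in any case recorded as adverse events (Protocol 12.3 and 12.4). What remains is a request for clarification.

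**Disagreement with the AESI tables.** The thresholds trigger referral and the AESI follows from judgment, so the two can differ legitimately even with the new row. A difference is not itself a defect.

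**Conclusion.** The point holds for the ACT and PEF summary tables. Followed as written, the SAP counts a subject whose only low ACT or PEF reading came at an unscheduled visit as not having crossed the threshold, and it gives no reason for omitting the kind of row it provides for laboratory data.

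The impact is modest. For PEF, each missed subject is worth 5 points with 20 per arm or 2 points with 50 per arm, assuming every subject has a post-baseline value and the tables are not split by asthma history. For ACT the step is larger but cannot be fixed from the documents. How often it would happen is unknown, since testing at unscheduled visits is optional. Neither the primary nor any secondary efficacy analysis is affected. The documents do not support extending the point to lost asthma events or to a failure of the ECG or physical-examination analysis.

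**What to change.** - Keep the by-visit rows in SAP 13.6.1 and 13.6.3.
- Add to the ACT and PEF tables (for PEF also by asthma history) one any/worst post-baseline row that includes unscheduled and early-termination visits. It should give the lowest ACT score, the lowest PEF as a percentage of predicted, and the number and percentage of subjects with any post-baseline ACT ≤19 or PEF <80%. The denominator is subjects with at least one post-baseline value.
- State in SAP 8.4 or 13 that early-termination results are included in the post-baseline safety summaries, including ECG.

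The cost is SAP wording and one extra row per table; no new data are needed. The drawback is that unscheduled testing is optional and unevenly timed, so an arm with more adverse-event visits has more chances to record a low value. Subjects who leave at relapse also have less time in which to record one. The any-time count should therefore be read beside the by-visit rows, and a footnote should say so.

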13.6.2. Respiratory Examination

A respiratory examination consists of medical interview. Questions regarding medical history of asthma, wheeze, dyspnea, and cough, will be performed for all subjects at Baseline/Day 1, Week 12, Week 24, Early Termination and Week 32/Follow-up questions are asked regarding:

- newly diagnosed (de novo) with Asthma / experience a worsening of Asthma since last visit
- newly diagnosed with Wheeze since last visit / experience a worsening of Wheeze since last visit
- newly diagnosed with Dyspnea since last visit / experience a worsening of Dyspnea since last visit
- newly diagnosed with Cough since last visit / experience a worsening of Cough since last visit

Only subjects reporting a medical history of asthma will require a respiratory examination at all visits. Subjects with a new (de novo) diagnosis of asthma will require a respiratory examination at all scheduled visits after the diagnosis is first made.

This document is confidential.

Newly diagnosed asthma or unexpected worsening of asthma are also reported as AESI. Respiratory examination questionnaire results will be listed on the Safety population.

13.6.3. Peak Expiratory Flow

Peak expiratory flow (PEF) testing during the clinical study will be performed under the supervision of qualified study personnel. Peak expiratory flow measurements should consist of 3 good efforts, with the best result documented. Obtained PEF values will be compared to predicted values based on the subject's age, sex and height.

PEF testing will be performed for all subjects at Baseline/Day 1, Week 12, Week 24, Early Termination, and Week32/Follow-up visits. For subjects reporting a medical history of asthma, PEF testing will be performed at all visits during the clinical study. For subjects diagnosed with new (de novo) asthma, PEF testing will be performed at all visits, starting with the visit in which the diagnosis was confirmed.

Following PEF parameters will be summarized as a continuous variable (Baseline and scheduled visits only):

- Actual peak expiratory flow rate
- Predicted peak expiratory flow rate
- Actual PEF of predicted value (%).

These PEF parameters will be summarized separately for the subset of subjects with and without history of asthma.

The number and percentage of subjects with PEF < 80% will be summarized by treatment group, visit (baseline and scheduled visits only), and medical history of asthma (with and without history of asthma).

All PEF results will be listed on the Safety population.

This document is confidential.

14. Changes from Analysis Planned in Protocol

- Summary Statistics will be presented by Treatment Group instead of “by Treatment Group and dosing regimen”.

This document is confidential.

15. Programming Considerations

All TFLs and statistical analyses will be generated using SAS® 9.4 or higher (SAS® Institute Inc., Cary, NC, USA) on a SAS Server. Changes to the software version (e.g. upgrades), or use of additional software consistent with the SAP will not be considered a violation of the SAP.

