## **Respiratory Assessments**

The results (absolute values and change from baseline) of PEF testing and respiratory examination will be summarized by visit, treatment group, and dose regimen. ACT for subjects with a medical history of asthma or newly-diagnosed asthma will be listed.

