8.1. General Methods

- All data will be listed, and summary tables will be provided.
- Unless otherwise specified, summaries will be presented for each treatment, if indicated, by visit.
- Continuous variables will be summarized using the number of observations (n), mean, standard deviation (SD), median, minimum and maximum. Categorical variables will be summarized using number of observations (n), frequency and percentages of subjects
- Unless otherwise stated, all statistical tests will be two-sided and conducted at the 5% level; all presented confidence intervals (CIs) will be two-sided 95% CIs.

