Header	Listing Number	Name	Analysis Set
	16.2.8.2.3	Physical Examination	Safety Population
	16.2.8.2.4	Respiratory Assessment – Medical Interview	Safety Population
	16.2.8.2.5	Respiratory Assessment – Peak Expiratory Flow (PEF)	Safety Population
	16.2.8.2.6	Known Asthma, Wheeze, Dyspnea and Cough Triggers	Safety Population
	16.2.8.2.7	Asthma Control Test (ACT)	Safety Population
	16.2.8.2.8	Subjects with a drop by >= 15% from Baseline for either PEF or ACT	Safety Population

This document is confidential.

20. Appendices

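### SAP 13.6.3 omits, without declaring it, the change-from-baseline summary of peak expiratory flow that protocol 14.4 requires

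*SAP*

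**What the plan says.** **Protocol 14.4, in its paragraph on respiratory measures, states:** "The results (absolute values and change from baseline) of PEF testing and respiratory examination will be summarized by visit, treatment group, and dose regimen".

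**SAP 13.6.3, Peak Expiratory Flow:** "Following PEF parameters will be summarized as a continuous variable (Baseline and scheduled visits only". The three parameters that follow are actual PEF, predicted PEF and actual as a percentage of predicted. The section adds separate summaries by asthma history, a count of subjects below 80% by arm, visit and asthma history, and a listing of all PEF results. It does not mention change from baseline.

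**Elsewhere in the SAP:**
- Where change from baseline is intended, the SAP tends to name it. For the Asthma Control Test (13.6.1): "ACT total score (absolute values and change from Baseline) will be summarized as a continuous variable (Baseline and scheduled visits only". For ECG (13.4): "All ECG data (absolute values and change from Baseline) will be summarized as continuous variables by visit (Baseline and scheduled visits only".
- The general rule in 8.1 does not add it: "Continuous variables will be summarized using the number of observations (n), mean, standard deviation (SD), median, minimum and maximum".
- The titles of the PEF tables in Section 17 (14.3.4.4.4 to 14.3.4.4.9) do not mention it.
- Section 14 declares one departure from the protocol, the loss of the split by dosing regimen, and nothing on PEF.
- Section 19 includes Listing 16.2.8.2.8: "Subjects with a drop by >= 15% from Baseline for either PEF or ACT". The listings there are described as tentative, and 13.6.3 does not refer to this one.

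Protocol Section 14 gives the SAP precedence where the two documents differ.

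**The concern.** New or worsening asthma is one of the important potential risks in protocol 5.3, which also reports a dose-dependent rise in asthma flares in an atopic dermatitis study. SAP 5.3 names PEF as a safety endpoint. It is the only numerical respiratory measure taken in every subject, since the Asthma Control Test is confined to those with asthma.

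The protocol asks for the within-subject view of PEF, and the governing document leaves it out without saying so. What is at stake is the by-arm description of how PEF moved from each subject's own starting point. The outputs that remain are raw means by visit, a count below a fixed threshold, and listings. None of them gives that description.

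**Working it through.** No figure in the documents can be reproduced here: neither gives a standard deviation, correlation or power for PEF. The check is a comparison of texts, followed by asking what the remaining outputs can show.

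**1. Is the omission real?** Protocol 14.4 names change from baseline for PEF; SAP 13.6.3 does not. SAP 8.1 and the table titles do not fill the gap, and SAP Section 14 does not declare it. With the SAP taking precedence, the summary is dropped.

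**2. Can raw visit means stand in for it?** For any visit t,

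mean at t (observed) − mean at baseline (all) = mean change (observed) + [baseline mean (observed) − baseline mean (all)].

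The bracket is a composition term. It is zero only if those measured at t had the same average baseline as everyone. Two features of the design work against that:
- *Asthma-only visits.* Footnote g of the Schedule of Assessments requires PEF at Weeks 4, 8, 16 and 20 only for subjects with a history of asthma or newly diagnosed asthma. All subjects are measured at Weeks 12 and 24. So at 4 of the 6 post-baseline treatment-period visits (4, 8, 12, 16, 20, 24) the overall table describes a subset. The table for subjects without asthma history would then hold, at those four visits, mainly newly diagnosed cases.
- *Relapse.* Relapsers leave the study (protocol 7.1). If relapse differs by arm, the arms are depleted differently.

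A change-from-baseline summary reports the first term on the right directly and drops the bracket. It does not remove selection in who is still observed.

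**3. Can the table of PEF below 80% stand in for it?** Count at t = newly below + already below at baseline and still below. Baseline is tabulated too, so, among the same subjects, count at t − count at baseline = newly below − recovered. That is a net figure, and new falls cannot be recovered from it.

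**4. What does the listing add?** It flags individual falls of at least 15%. It gives no count by arm and nothing on smaller falls. As an illustration, take a subject who goes from 120% to 90% of predicted:
- Relative fall: (120 − 90)/120 = 25%. The subject never crosses 80%, but meets the 15% rule.
- Effect on the mean of about 20 per arm (40 randomised 1:1): 30/20 = 1.5 points, and the same 1.5 points on mean change.

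The example therefore supports a per-arm count of falls of at least 15%. It does not support mean change over raw means.

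**5. Is change from baseline more precise?** With equal variances at the two visits and within-subject correlation ρ, SD(change)/SD(raw) = √(2(1 − ρ)). The values of ρ are assumptions:

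| ρ | SD(change)/SD(raw) |
|---|---|
| 0.3 | 1.18 |
| 0.5 | 1.00 |
| 0.7 | 0.77 |
| 0.8 | 0.63 |
| 0.9 | 0.45 |

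Change is more precise only if ρ exceeds 0.5, and less precise below that.

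**The case against.** The strongest reply is that this is a mismatch of wording with little consequence. Much of it stands, and it rules out several stronger readings.

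- *A reader might infer that a fall in an individual's lung function would go unseen.* The documents do not support that. Listing 16.2.8.2.8 flags falls of at least 15% from the subject's own baseline, and all PEF results are listed. Percent of predicted also takes out spread due to age, sex and height.
- *A reader might infer that the asthma risk is left unmonitored.* It is not. Low PEF or respiratory decline leads to referral (protocol 12.6.4), asthma is an event of special interest, the respiratory interview asks about new or worsening symptoms, and asthma events are adjudicated and tabulated by arm.
- *A reader might infer that PEF is the one measure left without change from baseline.* SAP 13.2.1 does not name it for urinalysis either. Protocol 14.4 also asks for it for the respiratory examination, for which SAP 13.6.2 plans only a listing of interview answers (Section 17 adds a summary table).
- *A reader might infer a definite loss of precision.* That depends on an unstated correlation, and the plan has no between-arm interval or test for PEF to which a precision figure could apply.

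It is also true that the protocol synopsis asks only for PEF summary tables, that protocol 6.2.2.2 lists only adverse events as safety endpoints, and that the SAP allows exploratory analyses and changes to its tentative outputs. So little is beyond recovery. Even so, the text that governs the analysis leaves out a summary that protocol 14.4 requires and does not say so, and no planned output replaces it by arm.

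**Conclusion.** The point holds as an undeclared omission from the SAP of a by-arm, by-visit safety summary required by protocol 14.4. That rests on the texts alone and needs no assumed number.

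The consequence is moderate. Individual falls can be found in listings, but nothing planned summarises them by arm. The tables that remain mix subjects: raw means change population at four of six treatment-period visits and as relapsers leave, and the below-80% counts combine new with pre-existing low values. How far the raw means would mislead depends on how baseline PEF differs between subjects with and without asthma and between relapsers and others, which the documents do not give. Over correlations of 0.9 to 0.3 the SD of change is 0.45 to 1.18 times the raw SD, so the case should not be argued on precision. The primary analysis is not affected.

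**What to change.** In SAP 13.6.3 and Tables 14.3.4.4.4 to 14.3.4.4.6:
- Add change from baseline in actual PEF and in percent of predicted, by visit and arm, with the number of paired observations. This restores what protocol 14.4 asks for.
- Add n (%) per arm with a post-baseline PEF fall of at least 15%, which is the SAP's own cut-off for Listing 16.2.8.2.8. State which visits count, including early termination and unscheduled ones, and refer to the listing from 13.6.3.

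In the below-80% tables (14.3.4.4.7 to 14.3.4.4.9), show subjects newly below 80% separately from those already below it at baseline.

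The second and third items go beyond the letter of protocol 14.4, but they are what makes individual falls readable by arm. If the omission was deliberate, SAP Section 14 should declare it and give the reason.

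The cost is some SAP wording and a few table rows. PEF is already scheduled at baseline and afterwards, so no new data are needed. The change should be made before unblinding.
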